#### ***10.1.4 Analysis Populations***

There will be 5 populations defined for this study: Safety, Clinical intent-to-treat (CITT), Microbiological intent-to-treat (MITT), Clinical per-protocol (CPP), and Microbiological per-protocol (MPP).

The **Safety population** will include all patients who received any study medication.

The **CITT population** will include all patients who were randomized.

The **MITT population** will include all CITT patients whose Visit 1 microbiological culture yields 1 or more pathogens, as defined in Section 7.1.2.

The **MITT-PA/SA population** will include the pathogen positive subset of the CITT population which includes all patients who received study medication and had culture positive for *P. aeruginosa* and/or *S. aureus* at baseline in the evaluable ear.

The **CPP population** will include all CITT patients who:

- Satisfied all inclusion and exclusion criteria;
- Did not receive any prohibited concomitant medications;
- Did not have any other major protocol violations;

- Completed Visit 3 and Visit 4 (unless the patient was deemed a clinical failure at an earlier visit than Visit 4); and
- Had compliance rates between 80% and 120% as defined in Section 10.1.8 (patients who are deemed Clinical Failures are to be included if they had compliance rates between 80% and 120% during the first 3 days of study treatment).

The **MPP population** will include all CPP patients whose Visit 1 microbiological culture yields 1 or more pathogens and who had microbiological results (when patient has material to culture) from Visit 3 and/or Visit 4 unless the patient was deemed a clinical failure at an earlier visit than Visit 4.

For the CITT and MITT populations, the treatment group of a patient will be determined by the treatment group to which the patient was randomized.

For the Safety, CPP and MPP populations, the treatment group of a patient will be determined by the treatment the patient received, not necessarily the group to which he or she was randomized. The Safety population will be used for all safety analyses.

The primary populations for efficacy analyses will be the MITT population.

The populations to be used for each of the secondary efficacy endpoints will be detailed in the Statistical Analysis Plan.

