4.4 Analysis Populations

There will be 6 populations defined for this study: Safety, Clinical intent-to-treat (CITT), Microbiological intent-to-treat (MITT), MITT-PA/SA, CPP, and MPP.

The **Safety population** will include all patients who received any study medication.

The **CITT population** will include all patients who were randomized.

The **MITT population** will include all CITT patients whose Visit 1 microbiological culture yields 1 or more pathogens, as defined in Section 4.7.2.

The **MITT-PA/SA population** will include the pathogen positive subset of the CITT population which includes all patients who received study medication and had culture positive for *P. aeruginosa* and/or *S. aureus* at baseline in the evaluable ear.

The **CPP population** will include all CITT patients who:

- Satisfied all inclusion and exclusion criteria;
- Had analysis results from Visit 1 otorrhea sample;
- Did not receive any prohibited concomitant medications. Note if a patient receives prohibited medication on or after receiving rescue medication and does not have any other major protocol deviations, the patient will be included in the CPP;
- Did not have any other major protocol violations;
- Completed Visit 3 and Visit 4 (unless the patient was deemed a clinical failure at an earlier visit than Visit 4);
- Had compliance rates between 80% and 120% as defined in Section 4.6 (patients who are deemed Clinical Failures are to be included if they had compliance rates between 80% and 120% during the first 3 days of study treatment); and
- Received at least 4 doses of study medication during the first 72 hours.

The **MPP population** will include all CPP patients whose Visit 1 microbiological culture yields 1 or more pathogens and who had microbiological results (when patient has material to culture) from Visit 2 and/or Visit 4 unless the patient was deemed a clinical failure at an earlier visit than Visit 4.

For the CITT, MITT and MITT-PA/SA populations, the treatment group of a patient will be determined by the treatment group to which the patient was randomized.

Effective Date: [REDACTED]
Related to: [REDACTED]

CONFIDENTIAL

Project Document Version No. 2.0
Project Document Effective Date: Date of last signature

Page 12 of 34

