4.7.2 Primary Efficacy Variable – *Therapeutic Response*

The primary endpoint for the assessment of efficacy is therapeutic response at Visit 3 in the MITT-PA/SA population. Efficacy analyses of the primary endpoint will also be conducted on the MITT, MPP CITT and CPP populations.

Therapeutic cure is the combined clinical and microbiological cure. Clinical and microbiological cure will be considered achieved if edema, otalgia, and otorrhea are resolved with no further requirement of antimicrobiological therapy and bacteriological response is Eradication or Presumed Eradication.

Overall Clinical Outcome is based on the Total Signs/Symptoms Scale (TSSS), which is calculated by the sum of otalgia score + edema score + otorrhea score. Clinical cure is a TSSS equal to 0.

Otalgia is the level of pain in the ear and is measured on a scale of 0 to 3. It will be assessed as:

- Severe (3) if it interferes with activities of daily living;
- Moderate (2) if it causes discomfort but does not interfere with activities of daily living;
- Mild (1) if there is awareness of pain but not much discomfort

- Absent (0) if there is total absence of pain.

Edema is the level of swelling in the ear and is measured on a scale of 0 to 3. It will be assessed as:

- Severe (3) if the tympanic membrane is not visible because of swelling;
- Moderate (2) if the tympanic membrane is partially visible;
- Mild (1) if there is some swelling but the tympanic membrane is fully visible;
- Absent (0) if there is no visible swelling.

Otorrhea is the discharge from the ear and is measured on a scale of 0 to 3. It will be assessed as:

- Severe (3),
- Moderate (2),
- Mild (1),
- Absent (0).

Bacteriological response will be categorized for each patient based on the microbiological culture results. Positive results will be categorized into three groups: target pathogen, non-target pathogen, and non-pathogen. For analysis purposes, patients with a target pathogen or non-target pathogen will be considered to be culture positive for a pathogen. Negative results and non-pathogen positive results will be considered to be culture negative for a pathogen. For any patient with a culture positive for a pathogen at Visit 1, bacteriologic response at Visits 3 will be classified as:

- Eradication if the culture does not show growth of any pathogen;
- Presumed Eradication if there is no material to culture and the Overall Clinical Outcome is Clinical Improvement or Clinical Cure as defined above;

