Overall Clinical Outcome is based on the TSSS, which is calculated by the sum of otalgia score + edema score + otorrhea score. Patients will be allocated to one of the following categories for Overall Clinical Outcome:

1. Clinical Cure: TSSS is 0
2. Clinical Improvement: TSSS is different than 0 but lower than the previous visit
3. Clinical Failure: TSSS does not meet the definitions of Clinical Cure or Clinical Improvement.
4. Indeterminate: Discontinued (for reasons other than Clinical Failure) or lost to follow-up

Overall clinical outcome will be summarized by treatment group and visit in terms of proportion in each category at each visit.

Responses will be categorized into two groups for analysis. Clinical improvement, Clinical Failure, and indeterminate will be collapsed into a single category: Clinical Failure. Overall clinical outcome will be analyzed using the same method as the primary efficacy endpoint. A Pearson’s Chi Squared test for independence will be used to test that there is no difference between the combined treatment and each individual component at Visits 3 and 4.

If a patient took rescue medication prior to Visit 3, the response will be considered a clinical failure at Visit 3. Similarly, if a patient took rescue medication prior to Visit 4, the response will be considered a clinical failure at Visit 4.

A by-patient listing of overall clinical outcome will be provided.

Microbiological Outcome

Microbiological Outcome is described in Section 4.7.2.

Microbiological outcome will be summarized by treatment group and visit in terms of proportion in each category at each visit.

If a patient took rescue medication prior to Visit 3, the response will be considered a failure at Visit 3. Similarly, if a patient took rescue medication prior to Visit 4, the response will be considered a failure at Visit 4.

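### The per-protocol sets used to support the Visit 3 primary endpoint require Visit 4 of patients cured at Visit 3 but waive it for clinical failures, so membership depends on the outcome being analysed

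*SAP*

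**What the plan says.** **Membership.** SAP 4.4 requires that a CPP patient "Completed Visit 3 and Visit 4 (unless the patient was deemed a clinical failure at an earlier visit than Visit 4"; protocol 10.1.4 has the same criterion. The MPP "will include all CPP patients whose Visit 1 microbiological culture yields 1 or more pathogens", so it inherits the rule.

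**Use.** SAP 4.7.2 defines the primary endpoint: "The primary endpoint for the assessment of efficacy is therapeutic response at Visit 3 in the MITT-PA/SA population". It then adds: "Efficacy analyses of the primary endpoint will also be conducted on the MITT, MPP CITT and CPP populations". Protocol 10.1.10.1 agrees. Neither document defines a separate per-protocol set for Visit 3 endpoints. SAP 4.3.2 uses the comparison across analysis populations to judge the impact of major protocol deviations.

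**Timing.** The schedules of observations place Visit 3 on Days 8 to 10 and Visit 4 on Days 15 to 17.

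**Meaning of clinical failure.** SAP 4.7.3 uses the term in two ways. In the four-level outcome it applies when the "TSSS does not meet the definitions of Clinical Cure or Clinical Improvement". For the two-group analysis, "Clinical improvement, Clinical Failure, and indeterminate will be collapsed into a single category: Clinical Failure". The CPP criterion does not say which is meant.

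**The concern.** Take two compliant patients who are both assessed at Visit 3 and then do not return. One was cured at Visit 3 and the other was a clinical failure. Their Visit 3 results are equally valid, yet the cure is removed from the Visit 3 per-protocol analysis and the failure stays. Inclusion therefore depends on the outcome being analysed, and on an event that happens after that outcome is fixed.

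The blinded data review before database lock does not remove the problem, because it conceals the treatment arm but not the outcome. At stake is the interpretation of the robustness check. A per-protocol result that differs from the MITT-PA/SA result, or agrees with it, could partly reflect Visit 4 attendance rather than adherence to the protocol.

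**Working it through.** **Inputs from the documents (SAP 4.10).** Cure is assumed to be 62% on ciprofloxacin, raised by a relative 25% on the combination: 0.62 × 1.25 = 0.775, stated as 78%. The plan has 150 evaluable patients per group, two-sided 5% significance and 80% power, and expects about 80% of enrolled patients to complete the study. No cure rate is assumed for fluocinolone alone, so only the comparison with ciprofloxacin can be illustrated.

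**The plan's own figure.** With pooled variance under the null, 62% vs 77.5% needs 137 per group, and the continuity correction brings this to 150. The stated 150 is reproduced. It is not in dispute; the check only confirms the planning rates.

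**Assumed input.** Let m be the share of Visit 3 cures who miss Visit 4. The documents do not give it. I use 5% to 20%. The upper end is borrowed from expected overall non-completion (100% − 80%), which also covers patients withdrawn as failures and losses before Visit 3. It is not a Visit 3-to-Visit 4 figure.

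**Reading A: collapsed category, every non-cure exempt.** With true Visit 3 cure rate c,

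per-protocol rate = c(1 − m) / [c(1 − m) + (1 − c)].

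For c = 0.78 and m = 0.05: 0.741 / (0.741 + 0.22) = 0.771. For c = 0.62 and m = 0.05: 0.589 / (0.589 + 0.38) = 0.608.

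| m, combination | m, ciprofloxacin | Combination | Ciprofloxacin | Difference (points) | Odds ratio |
|---|---|---|---|---|---|
| 0 | 0 | 78.0% | 62.0% | 16.0 | 2.17 |
| 5% | 5% | 77.1% | 60.8% | 16.3 | 2.17 |
| 10% | 10% | 76.1% | 59.5% | 16.7 | 2.17 |
| 20% | 20% | 73.9% | 56.6% | 17.3 | 2.17 |
| 5% | 20% | 77.1% | 56.6% | 20.5 | 2.58 |
| 20% | 5% | 73.9% | 60.8% | 13.1 | 1.83 |

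The rule multiplies the cure odds in each arm by (1 − m), so equal m leaves the odds ratio unchanged. The last two rows need a 15-point imbalance between arms in Visit 4 attendance among cures. With the same imbalance and both arms truly at 62%, the per-protocol rates would be 60.8% and 56.6%, a spurious difference of 4.2 points.

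**Reading B: four-level category.** Improved patients who miss Visit 4 are now dropped as well. With proportions cured c, improved i and failed f, and missed-visit shares m_c and m_i,

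per-protocol rate = c(1 − m_c) / [c(1 − m_c) + i(1 − m_i) + f].

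This lies below c only when m_c(1 − c) exceeds i·m_i. The documents give no split of the non-cures; assume 62/30/8%.

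- m_c = m_i = 20%: 0.496 / (0.496 + 0.24 + 0.08) = 0.496 / 0.816 = 60.8%, a fall of 1.2 points. Reading A gives 56.6%, a fall of 5.4 points.
- m_c = 5%, m_i = 20%: 0.589 / (0.589 + 0.24 + 0.08) = 0.589 / 0.909 = 64.8%, a rise of 2.8 points.

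**Visit 3 completion only.** Missing Visit 4 then has no effect, and the rates stay at 78% and 62%.

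**The case against.** **The waiver has a purpose.** Patients stopped as treatment failures around Visit 2 are withdrawn (protocol 4.1, 8.2.2) and cannot attend Visit 4. Without the waiver they would be lost and the per-protocol cure rate inflated. This stands as a reason to keep failures. It gives no reason to require Visit 4 of cures when the endpoint is Visit 3.

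**The sets are only supportive.** This stands. Protocol 10.1 lists the MPP among the primary efficacy populations, so a reader might infer that the main result is exposed. Protocol 10.1.10.1 and SAP 4.4 and 4.7.2 place the primary analysis in MITT-PA/SA, which has no visit-completion rule. MITT, CITT and complete-case analyses are also planned, and protocol 10.1.5 provides a listing of exclusions with reasons, so exclusions due to Visit 4 would be visible.

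**The collapsed reading is the less natural one.** SAP 4.7.3 introduces it for analysing clinical outcome, not for eligibility. Applied to the CPP, it could exempt even patients lost before Visit 3, because they are indeterminate. This is a fair argument for the four-level reading, but the criterion does not say so, and under either reading cures are dropped and failures kept.

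**One set for all endpoints is a common convention.** That is true, but here the set's visit requirement interacts with an outcome-based waiver.

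**Conclusion.** The point holds for the supportive analyses of the Visit 3 endpoint: CPP and MPP membership depends on outcome and on attendance after the endpoint. It should be corrected, but it does not threaten the confirmatory test.

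A reader might infer that per-protocol cure rates are biased downward in every arm. The documents do not support that as a general statement. It follows under the collapsed category once some cures in each arm miss Visit 4; under the four-level category the shift is smaller in the equal-dropout example and can reverse.

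A reader might also infer a large distortion of the treatment difference. With equal dropout the illustration adds only 0.3 to 1.3 points to the planned 16.0. Larger shifts need unequal Visit 4 attendance by arm, and nothing in the documents of this double-blind trial indicates that. All magnitudes rest on assumed dropout, and those under the four-level reading also on an assumed outcome split.

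**What to change.** In SAP 4.4 and protocol 10.1.4, tie the visit requirement to the endpoint:

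- **Visit 3 endpoints:** CPP and MPP require completion of Visit 3, keeping the exemption for patients deemed failures earlier. The MPP also requires Visit 3 culture results when there is material to culture.
- **Visit 4 and sustained endpoints:** add completion of Visit 4, with the failure exemption.
- **Time to end of ear pain:** state which of the two sets applies.
- **Definition:** state that clinical failure in these criteria means the four-level category or discontinuation as a treatment failure, not the collapsed group.
- **Same edit:** reconcile the MPP culture requirement. The SAP asks for results from Visit 2 and/or Visit 4, the protocol from Visit 3 and/or Visit 4. Visit 2 is a telephone call with no culture scheduled.

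The compliance criterion also depends on outcome, since "patients who are deemed Clinical Failures are to be included if they had compliance rates between 80% and 120% during the first 3 days". This change does not remove that, and the report should say so when interpreting the per-protocol results.

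The cost is wording in two documents, a second per-protocol flag and a little more programming, all before database lock. No additional data are needed.

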#### 7.1.2 *Microbiological Efficacy Parameters*

Microbiological cultures of ear discharge will be taken at Visit 1; and in addition at visits 3 and 4 when discharge is present. The otorrhea sample will be taken prior to the debridement of the affected ear(s). A central laboratory will provide microbiological sampling kits with standardized instructions for sample preparation. The entrance to the ear canal will be swabbed with a cotton swab to remove any debris that could cause contamination. The ear canal may be irrigated if that is standard practice at the study site; irrigation must be documented in the EDC. An ACT II Transport Tube, as provided in the microbiological sampling kit, will be gently rubbed against the sides of the ear canal to obtain a suitable specimen for culture. Samples will be shipped to the central laboratory for processing. The central laboratory will be blinded to the treatment assignment of the patient from whom the sample was taken.

The central laboratory will use standardized clinical microbiological laboratory procedures (aerobic cultures only) to identify bacteria by species. Bacterial abundance will be assessed on a scale of 1+ to 4+, per standard laboratory grading (score=0 if the culture is sterile). To be considered a pathogen, the cultured organism must be present at a level of 1+ or higher.

The following species are most likely to be pathogens: *Pseudomonas aeruginosa*, *Staphylococcus aureus*, *Streptococcus* (primarily beta-hemolytic strains), and Gram-negative enteric bacilli (e.g., *Enterobacter*, *Proteus*, and *Klebsiella* species).

The following bacteria are generally colonizers and will not be categorized as pathogens: alpha-hemolytic streptococci, coagulase-negative staphylococci, *Bacillus* species, *Corynebacterium* species, *Lactobacillus* species, and *Propriionobacterium* species. Fungi and yeasts will not be considered as pathogens.

The culture results will be classified in the following groups:

- Negative: culture does not show any growth
- Positive: culture shows microorganism growth
  - Positive with non-pathogens: microorganism are generally colonizers and /or are not categorized as pathogens
  - Positive with pathogens:
    - Target pathogen: *P. aeruginosa* and/or *S. aureus*

- Non-target pathogens: pathogens different to *P. aeruginosa* and/or *S. aureus*

For any patient with a culture positive for a pathogen at Visit 1, bacteriologic response at Visits 3 will be classified as:

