### 8.2.2 Visit 2 (Phone Visit)

A study staff member will telephone each patient or caregiver on Day 3 or Day 4 of treatment. The information obtained at this “phone visit” will be recorded in the Visit 2 page of the EDC. Study staff will ask about and record any AEs and any changes in concomitant medications since Visit 1. Study staff will also ask about study medication compliance. Patients or caregivers will also be asked if otitis symptoms are improving or worsening. A specific questionnaire to obtain all these information will be used.

Patients who report no improvement in otitis symptoms will be asked to come in for an unscheduled visit as soon as possible. At this visit, the Investigator will choose one of the two following options for the patient:

1. Continue the patient in the study. The present visit will be recorded as an unscheduled visit. The patient should continue taking study medication without interruption. A debridement of the ear and placement of otowick may be needed.
2. Discontinue study medication. The present visit will be recorded as Visit 3, the End of Treatment visit. The patient will be withdrawn from the study and may be treated with other medication (standard treatment) as appropriate at investigator's discretion. The clinical outcome for the patient will be recorded as Treatment Failure.

If a patient has unilateral AOE at baseline, but develops AOE of the contralateral ear subsequently during the study, then at Visit 2 or at unscheduled visit prior to Visit 3, the investigator or designee will obtain a second kit number (with the same medication) through the IWRs to treat the contralateral ear. This information will be included in the Comments page and Resupply or replacement page of the EDC, and will not be considered as an AE.

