3.2 Efficacy and Safety Variables

The primary efficacy variable is therapeutic response at Visit 3. Therapeutic response is the combined overall clinical outcome and the overall microbiological outcome.

The secondary efficacy variables include:

- Time to end of ear pain
- Sustained microbiological cure
- Overall Clinical Outcome at Visits 3 and 4
- Microbiological response at Visits 1, 3, and 4
- Therapeutic response at Visit 4
- Brighton grading at Visits 1, 3, and 4
- Otorrhea at Visits 1, 3, and 4
- Otalgia at Visits 1, 3, and 4
- Edema at Visits 1, 3, and 4

The safety variables include AEs reported throughout the study, vital signs (temperature, blood pressure, and heart rate) at Visits 1, 3, and 4, and physical examination at Visit 1.

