Appendix 1 Schedule of Observations

Table 2 Schedule of Observations

Evaluation	Visit 1 Screening/ Study Entry	Visit 2 By Telephone	Visit 3 End of Treatment	Visit 4 Post- Treatment Follow-Up
Study Day	1	3-4	8-10 or within 2 days of early termination	15-17
Informed Consent (and Assent Form when applicable)	X			
Inclusion/exclusion criteria	X			
Medical history	X			
Concurrent symptoms/conditions	X			
Urine pregnancy test ^a	X			
Physical examination	X			
Vital signs ^b	X		X	X
Brighton grading	X		X	X
Ear pain	X		X	X
Edema	X		X	X
Ototorhea	X		X	X
Overall Clinical Outcome			X	X
Microbiological culture of ear discharge ^c	X		X	X
Register patient visit through IWRS	X	X	X	X
Randomization through IWRS	X			
Dispense study medication and explain its use	X	X ^d		
Collect used and unused study medication containers			X ^e	
Dispense patient diary and explain its use	X			
Inquire about otitis symptoms		X ^f		
Review patient diary			X	X
Concomitant medications	X	X	X	X
Adverse events	X	X	X	X

^a For female patients of childbearing potential.

^b To include temperature, blood pressure, and pulse rate.

^c If no discharge is present, no attempt to culture will be made.

^d If patient with unilateral AOE at baseline becomes bilateral prior to Visit 3 a resupply study medication kit (with the same medication) will be dispensed^e

If patients forget to bring in containers at Visit 3, they must bring them in no later than Visit 4.

^e If patients report no improvement in otitis symptoms, they will be asked to come in for a visit as soon as possible. At this visit, they may prematurely discontinue study treatment (in which case the visit will be recorded as Visit 3, the End of Treatment visit) or continue study treatment (in which case the visit will be recorded as an unscheduled visit).

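### SAP 4.4 ties the microbiological per-protocol set to results from Visit 2, a telephone call with no culture, where protocol 10.1.4 says Visit 3 (wrong as written, minor)

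*SAP*

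**What the plan says.** SAP 4.4 builds the MPP set from clinical per-protocol (CPP) patients whose Visit 1 culture grew at least one pathogen. It then asks for microbiological results, where there was material to culture, "from Visit 2 and/or Visit 4 unless the patient was deemed a clinical failure at an earlier visit than Visit 4". Protocol 10.1.4 has the same rule with a different visit: "from Visit 3 and/or Visit 4 unless the patient was deemed a clinical failure at an earlier visit than Visit 4".

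Both documents show what happens at Visit 2. Protocol 8.2.2: "A study staff member will telephone each patient or caregiver on Day 3 or Day 4 of treatment". The SAP schedule (Appendix 1) heads the column "Visit 2 By Telephone" and marks the culture row only for Visits 1, 3 and 4. Protocol 7.1.2 gives the culture visits: "Microbiological cultures of ear discharge will be taken at Visit 1; and in addition at visits 3 and 4 when discharge is present". SAP 3.2 lists as a variable "Microbiological response at Visits 1, 3, and 4".

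On the use of the set, SAP 4.7.2 states: "The primary endpoint for the assessment of efficacy is therapeutic response at Visit 3 in the MITT-PA/SA population". It then adds: "Efficacy analyses of the primary endpoint will also be conducted on the MITT, MPP CITT and CPP populations". SAP 4.3.2 has patients assigned to the sets of section 4.4 at a blinded data review before database lock.

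**The concern.** The MPP rule names a visit that cannot supply the data it asks for. Read literally, only Visit 4 culture results count towards membership, and the Visit 3 culture, which belongs to the visit of the primary endpoint, plays no part.

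This is an operative rule. The blinded review is to apply section 4.4, so a team that follows the SAP to the letter would build a different set from one that follows the protocol. The Visit 3 therapeutic response is repeated in MPP, and SAP 4.3.2 relies on comparing analysis populations to judge robustness to major deviations. At stake is whether that supportive comparison uses the set the protocol defined.

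**Working it through.** The plan gives no figure to reproduce here, so the check compares the two rules on every possible pattern of culture data.

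**Step 1. Can a Visit 2 culture exist?** The scheduled visit is a telephone call. If the patient reports no improvement and is seen in person, protocol 8.2.2 has that visit recorded either as unscheduled or, if study medication is stopped, as Visit 3. Neither creates a Visit 2 culture, so the SAP rule reduces to Visit 4.

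**Step 2. Is it a deliberate change?** SAP 4.4 does add CPP criteria that protocol 10.1.4 lacks, such as a minimum number of doses in the first 72 hours. But a change to a visit without cultures would serve no purpose, and SAP 4.11 does not list one. A typing error is the likely explanation.

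**Step 3. Compare the rules.** Take CPP patients with a Visit 1 pathogen who are not exempt as earlier clinical failures. Give each visit one of three states: result available, no material to culture, or material present but result missing. The qualifier about material is read as follows: the rule is met if any named visit has a result, or if no named visit has material with a missing result. The protocol rule uses Visits 3 and 4; the SAP rule in effect uses Visit 4 only.

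| Visit 3 | Visit 4 | Protocol | SAP | Agree? |
|---|---|---|---|---|
| result | result | in | in | yes |
| result | no material | in | in | yes |
| result | missing | in | out | **no (a)** |
| no material | result | in | in | yes |
| no material | no material | in | in | yes |
| no material | missing | out | out | yes |
| missing | result | in | in | yes |
| missing | no material | out | in | **no (b)** |
| missing | missing | out | out | yes |

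The rules differ on 2 of 9 combinations. This counts patterns, not patients. With Visit 3 in place of Visit 2 the two rules are the same and all nine agree.

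**Step 4. What are these patients' Visit 3 outcomes?** Cultures after baseline are taken only when discharge is present, so (a) and (b) both imply discharge at Visit 3:

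- discharge means an otorrhea score of at least 1;
- the total signs/symptoms score (TSSS) is otalgia + edema + otorrhea, so TSSS is at least 1;
- therapeutic cure needs TSSS = 0 (protocol 7.1.3, SAP 4.7.2).

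Every affected patient is therefore a therapeutic failure at Visit 3, whatever the culture showed. The SAP wording removes such failures from the MPP denominator in (a) and adds them in (b). In (a), an actual Visit 3 bacteriological result is also lost from the MPP analysis of microbiological outcome. In (b), a clinically improved patient enters with an Indeterminate Visit 3 bacteriological response.

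**Step 5. Who is exempt?** Both rules exempt a patient judged a clinical failure before Visit 4. On the four-category outcome (SAP 4.7.3), a patient with discharge at Visit 3 may be Clinical Improvement and so not exempt; (a) and (b) are then patients improved, but not cured, at Visit 3. For analysis, SAP 4.7.3 also collapses Clinical Improvement and Indeterminate into failure. If the exemption used that two-level class, every patient with Visit 3 discharge would be exempt under both rules, and the two differences would vanish. The documents do not say which class applies.

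**The case against.** The strongest case against giving this weight is that it is an obvious slip in a supportive set. The SAP elsewhere gives microbiological response only at Visits 1, 3 and 4, so a careful programmer would probably notice. MPP is nested in CPP, which still requires Visits 3 and 4 to be completed unless the patient failed earlier; only the Visit 3 culture result is disregarded, not the visit. On the two-level reading of clinical failure the slip has no effect. All of this stands and limits the size. It does not make the sentence right, because the blinded review is told to apply section 4.4.

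A reader might infer four stronger things, none of which the documents support:

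- That the SAP wording lets in patients whose Visit 3 culture was lost but who have a Visit 4 result. Under the protocol's and/or they are included as well.
- That the correction would make membership depend on having the Visit 3 result. It would not; a Visit 4 result alone still qualifies. The case is for restoring the protocol's rule, not tightening it.
- That the affected patients count as failures only because indeterminate outcomes are treated as failures. They already fail on TSSS.
- That the primary result is in doubt, or that the per-protocol check as a whole uses the wrong patients. Protocol 10.1 does list MPP among the primary efficacy populations, but protocol 10.1.10.1 and SAP 4.7.2 place the primary test in MITT-PA/SA, and the SAP uses MPP as an additional analysis.

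**Conclusion.** The MPP rule in SAP 4.4 is wrong as written: it names a visit with no culture and contradicts protocol 10.1.4. The severity is minor. Two patterns of missing culture results are classified differently, and all the patients concerned are Visit 3 therapeutic failures. The effect on the Visit 3 analysis is to move some non-cures in or out of the MPP denominator. No patient's outcome is altered, and the MITT-PA/SA primary test, its alpha and the sample size are untouched.

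The documents do not give the number affected. It is probably small, since it needs discharge at Visit 3, a missing culture result at Visit 3 or Visit 4, and no exemption as an earlier failure. The conclusion that the rules conflict rests on the text alone. The count of two patterns rests on the reading of the material qualifier in step 3 and on the four-category meaning of clinical failure; with the two-level meaning the practical effect is nil.

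**What to change.** In the MPP definition of SAP 4.4, replace Visit 2 and/or Visit 4 with Visit 3 and/or Visit 4, as in protocol 10.1.4. The cost is one digit and a line in the SAP's change record. It should be done before patients are assigned to analysis sets at the blinded data review. No other analysis, table or sample-size statement needs to change.
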